9.2. Treatment modification

The treatment modifications listed in this section are for reference only. The investigator should modify the treatment according to clinical judgement and best medical practices.

Event	Severity	Action
Angioedema	Any	Stop study drug permanently
Anaphylaxis	Any	Stop study drug permanently
Generalized Rashes	Any	- Stop study drug for two weeks - Consider to rechallenge at next follow up/ assessment if the rash is mild, or unlikely to be related to study drug
Epigastric discomfort	Mild	- Reduce dose to 100 mg of study drug - Start PPI - Review in one month. If symptoms persist, consider stopping study drug and gastroscopy (Treat as per Gastroscopic findings)
Epigastric discomfort	Moderate	- Stop study drug - Start PPI - Review in one month - Rechallenge with lower dose (i.e. 100 mg) of study drug if symptoms resolved and continue long term PPI therapy. - Consider gastroscopy if symptoms persist
Epigastric discomfort	Severe	- Stop study drug - Start PPI - Gastroscopy - Treat as per Gastroscopic findings
Haematemesis	-	- Stop study drug permanently - Start PPI - Gastroscopy - Treat as per Gastroscopic findings
Melenic stools	-	- Stop study drug permanently - Start PPI - Gastroscopy with/without colonoscopy - Treat as per Gastroscopic findings
Asymptomatic drop in haemoglobin of > 2 g/dL from baseline	-	- Stop study drug - Start PPI - Gastroscopy/Colonoscopy - Treat as per Gastroscopic findings

Gastroscopic Findings

Event	Severity	Action
Gastritis	Mild/ Moderate	- Stop study drug - Start PPI - Rechallenge with lower dose (i.e. 100 mg) of study drug 2- 4 weeks after therapy with PPI - Helicobacter pylori eradication if present
Gastritis	Severe	- Stop study drug (for 4-8 weeks) - Start with PPI

		
 - Consider rechallenge with lower dose (i.e. 100 mg) of study drug 4-8 weeks after therapy with PPI if symptoms resolved completely - Helicobacter pylori eradication if present
Peptic ulcer	-	
 - Stop study drug permanently - Start PPI - Helicobacter pylori eradication if present
Oesophageal or Gastric Varices	-	
 - Stop study drug permanently - Continue on follow up as per institutional practice - Helicobacter pylori eradication if present

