11.2. Baseline

- Medical history: asthma, diabetes, ischaemic heart disease, stroke, gastrointestinal ulcers or bleeding, alcohol history, smoking
- Tumour History: stage, risk factors, treatment, and tumour response grade (for patients with neoadjuvant chemoradiation only)
- Family history of Colorectal cancer
- Record ongoing medication
- Vital signs: body weight, height, BP
- Haematology: haemoglobin (within 8 weeks prior to randomisation)
- CEA(latest reading)
- Randomization performed and study treatment commence

11.3. 3-monthly assessments

3-monthly patient assessments will be done at month 3, 6, 9, 12, 15, 18, 21, 24, 27, 30, 33, and 36. Assessments \pm 1 month window will be allowed for each 3-monthly visit. Phone assessments are allowed at alternate 3-monthly assessments if patient is unable to return for site follow-up. The following will be performed at each assessment:

- CEA
- Hb (for month 6, 12, 18, 24, 30, 36 only)
- Record AE and SAE (See Section 13.2)
- Concomitant medication
- Concomitant NSAIDs
- Medical Events : (acute myocardial infarction, transient ischemic attack, stroke, new cancers and gastrointestinal bleeding)
- Recurrence and Salvage Chemotherapy

The following will be performed at each specified interval:

- Surveillance Colonoscopy/ CT colonogram at month 6 and 30 (optional) *
- Surveillance CT scan (abdomen \pm pelvis) / or CT colonogram at month 6, 18 and 30 (optional)*

Off-site investigations (for example surveillance CEA, CT scan, colonoscopy) will be allowed and data from unscheduled investigations (for example CT scan or colonoscopy due to symptoms or during hospitalisations) may be recorded.

* The policy of surveillance CT scan and Colonoscopy (as described above) will be decided at the study centre level, by the study centre PI. However, these procedures wherever implemented, should be consistently applied to all trial subjects within a particular study centre.

Early Treatment Discontinuation follow-up

- Subjects with early treatment discontinuation (e.g. for toxicity) but without recurrence will continue with the same 3 monthly assessments except Hb that is not required after study drug treatment is discontinued.

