11.7. Assessment of Medical Events

Medical events such as acute myocardial infarction, ischemic stroke (including transient ischemic attack), hemorrhagic stroke or new non-colorectal cancers will be recorded. Major gastrointestinal bleeding (requiring blood transfusion) will also be recorded.

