4.7 Safety Endpoints

The evaluation of drug safety is based on clinical adverse events and laboratory abnormalities reported during the study. All safety presentations will be based on actually-treated subject dataset.

AEs and SAEs will be summarised using the following method:

Number and percentage of subjects who ever reported adverse event (AE) and serious adverse event (SAE) together with the number of AEs and SAEs will be presented by treatment group. The severity and outcome of AEs and SAEs, relationship to treatment and action taken will be summarised.

Same AE term reported at multiple level of severities by a single subject will be counted for each level of severity, not just the highest severity. Under subject counts at each severity category, only unique subject will be counted. The same method will also be applied for summaries by relationship, treatment given, outcome, and action taken.

All on-study adverse events will be further summarised by MedDRA terminology. Summaries of AEs will be based on the resulting system organ class (SOC) and preferred terms (PT). All reported SAEs will be listed indicating the subject ID, SAE criteria, randomisation date, onset date, resolution date, relationship to study treatment and outcome of causality.

The term “AEs” used in the summaries would cover severe AEs and SAEs as well.

Number of subjects who ever experienced the following medical events including acute myocardial infarct, ischaemic stroke, new cancer (non-colorectal), major GI bleeding (requiring blood transfusion), haemorrhagic stroke and major nervous system bleeding throughout the study will be counted and its corresponding percentages will be respectively compared between the two treatment groups using Fisher’s exact test.

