Appendix 1: Mock-up tables

Table 1: Subject status and demographics

	Modified intention-to-treat			Per-protocol		
	Aspirin	Placebo	Total	Aspirin	Placebo	Total
Number of subjects randomised	xxx	xxx	xxx	xxx	xxx	xxx
Number of subjects ineligible but randomised, n (%)	xx (xx.x)	xx (xx.x)	xx (xx.x)	xx (xx.x)	xx (xx.x)	xx (xx.x)
Subjects discontinued study treatment, n (%)	xx (xx.x)	xx (xx.x)	xx (xx.x)	xx (xx.x)	xx (xx.x)	xx (xx.x)
Completed protocol treatment	xx (xx.x)	xx (xx.x)	xx (xx.x)	xx (xx.x)	xx (xx.x)	xx (xx.x)
AE/SAE	xx (xx.x)	xx (xx.x)	xx (xx.x)	xx (xx.x)	xx (xx.x)	xx (xx.x)
Protocol violation/ ineligibility	xx (xx.x)	xx (xx.x)	xx (xx.x)	xx (xx.x)	xx (xx.x)	xx (xx.x)
Clinical decision	xx (xx.x)	xx (xx.x)	xx (xx.x)	xx (xx.x)	xx (xx.x)	xx (xx.x)
Subject decision	xx (xx.x)	xx (xx.x)	xx (xx.x)	xx (xx.x)	xx (xx.x)	xx (xx.x)
Recurrence	xx (xx.x)	xx (xx.x)	xx (xx.x)	xx (xx.x)	xx (xx.x)	xx (xx.x)
Death	xx (xx.x)	xx (xx.x)	xx (xx.x)	xx (xx.x)	xx (xx.x)	xx (xx.x)
Others	xx (xx.x)	xx (xx.x)	xx (xx.x)	xx (xx.x)	xx (xx.x)	xx (xx.x)
Subjects who did not complete study, n (%)	xxx (xx.x)	xxx (xx.x)	xxx (xx.x)	xxx (xx.x)	xxx (xx.x)	xxx (xx.x)
Subject withdrew consent	xx (xx.x)	xx (xx.x)	xx (xx.x)	xx (xx.x)	xx (xx.x)	xx (xx.x)
Withdrawn from study by investigator	xx (xx.x)	xx (xx.x)	xx (xx.x)	xx (xx.x)	xx (xx.x)	xx (xx.x)
Lost to follow-up	xx (xx.x)	xx (xx.x)	xx (xx.x)	xx (xx.x)	xx (xx.x)	xx (xx.x)
Death	xx (xx.x)	xx (xx.x)	xx (xx.x)	xx (xx.x)	xx (xx.x)	xx (xx.x)
Others	xx (xx.x)	xx (xx.x)	xx (xx.x)	xx (xx.x)	xx (xx.x)	xx (xx.x)

Subject follow-up completion, n (%)

1 year follow-up	XX (XX.X)	XX (XX.X)	XX (XX.X)	XX (XX.X)	XX (XX.X)	XX (XX.X)
2 year follow-up	XX (XX.X)	XX (XX.X)	XX (XX.X)	XX (XX.X)	XX (XX.X)	XX (XX.X)
3 year follow-up	XX (XX.X)	XX (XX.X)	XX (XX.X)	XX (XX.X)	XX (XX.X)	XX (XX.X)
4 year follow-up	XX (XX.X)	XX (XX.X)	XX (XX.X)	XX (XX.X)	XX (XX.X)	XX (XX.X)
5 year follow-up	XX (XX.X)	XX (XX.X)	XX (XX.X)	XX (XX.X)	XX (XX.X)	XX (XX.X)

Subject follow-up time, month

Mean (SD)	XX.X (XX.X)	XX.X (XX.X)	XX.X (XX.X)	XX.X (XX.X)	XX.X (XX.X)	XX.X (XX.X)
Median (IQR)	XX.X (XX.X)	XX.X (XX.X)	XX.X (XX.X)	XX.X (XX.X)	XX.X (XX.X)	XX.X (XX.X)
Min, Max	XX.X, XX.X	XX.X, XX.X	XX.X, XX.X	XX.X, XX.X	XX.X, XX.X	XX.X, XX.X

Demographics

Age, year

n	XXX	XXX	XXX	XXX	XXX	XXX
Mean (SD)	XX.X (XX.X)	XX.X (XX.X)	XX.X (XX.X)	XX.X (XX.X)	XX.X (XX.X)	XX.X (XX.X)
Median (IQR)	XX.X (XX.X)	XX.X (XX.X)	XX.X (XX.X)	XX.X (XX.X)	XX.X (XX.X)	XX.X (XX.X)

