Country Y vs. Reference Country	xx.x (xx.x-xx.x)	0.xxx	xx.x (xx.x-xx.x)	0.xxx

Tumour type					
Rectal cancer vs. Dukes C colon cancer			0.xxx		0.xxx
High risk Dukes B colon cancer vs. Dukes C colon cancer	xx.x (xx.x-xx.x)		0.xxx	xx.x (xx.x-xx.x)	0.xxx
Adjuvant chemotherapy (exposed vs. not exposed to Oxaliplatin)	xx.x (xx.x-xx.x)		0.xxx	xx.x (xx.x-xx.x)	0.xxx

Note: Adjusted hazard ratio was estimated using Cox proportional hazard model with trial stratification factors (centre pooled by country (categorical), type of tumour (categorical) and type of adjuvant chemotherapy (categorical)) as covariates.

Table 9: Summary of adverse events

Population: Safety population

	Number of Subjects		Number of Events	
	Aspirin (N=xxxx)	Placebo (N=xxxx)	Aspirin	Placebo
Subjects ever experienced any AE, n (%)	xxx (xx.x)	xxx (xx.x)	xxx	xxx
Severity, n (%)				
Mild	xxx (xx.x)	xxx (xx.x)	xxx	xxx
Moderate	xxx (xx.x)	xxx (xx.x)	xxx	xxx
Severe	xxx (xx.x)	xxx (xx.x)	xxx	xxx
Unknown	xxx (xx.x)	xxx (xx.x)	xxx	xxx
Treatment related, n (%)				
Not related	xxx (xx.x)	xxx (xx.x)	xxx	xxx
Unlikely related	xxx (xx.x)	xxx (xx.x)	xxx	xxx
Possibly related	xxx (xx.x)	xxx (xx.x)	xxx	xxx
Probably related	xxx (xx.x)	xxx (xx.x)	xxx	xxx
Definitely related	xxx (xx.x)	xxx (xx.x)	xxx	xxx
Unknown	xxx (xx.x)	xxx (xx.x)	xxx	xxx
Treatment given, n (%)				
Yes	xxx (xx.x)	xxx (xx.x)	xxx	xxx
No	xxx (xx.x)	xxx (xx.x)	xxx	xxx
Outcome, n (%)				
Recovered	xxx (xx.x)	xxx (xx.x)	xxx	xxx
Recovered with sequelae	xxx (xx.x)	xxx (xx.x)	xxx	xxx
Ongoing	xxx (xx.x)	xxx (xx.x)	xxx	xxx
Death	xxx (xx.x)	xxx (xx.x)	xxx	xxx
Unknown	xxx (xx.x)	xxx (xx.x)	xxx	xxx
Action taken to study treatment, n (%)				
None	xxx (xx.x)	xxx (xx.x)	xxx	xxx
Modified	xxx (xx.x)	xxx (xx.x)	xxx	xxx
Temporarily interrupted	xxx (xx.x)	xxx (xx.x)	xxx	xxx
Permanently discontinued	xxx (xx.x)	xxx (xx.x)	xxx	xxx
Unknown	xxx (xx.x)	xxx (xx.x)	xxx	xxx

AE: adverse event.

Note: Under number of events, the same AE term of multiple severities, relationships, treatments, actions reported by a single subject will be counted separately. Under number of subjects, only unique subjects will be counted.

Table 10: Summary of serious adverse events

Population: Safety population

	Number of Subjects		Number of Events	
	Aspirin (N=xxxx)	Placebo (N=xxxx)	Aspirin	Placebo
Subjects ever experienced any SAE, n (%)	xxx (xx.x)	xxx (xx.x)	xxx	xxx
SAE criteria, n (%)				
Death	xxx (xx.x)	xxx (xx.x)	xxx	xxx
Life-threatening	xxx (xx.x)	xxx (xx.x)	xxx	xxx

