Inpatient hospitalization	xxx (xx.x)	xxx (xx.x)	xxx	xxx
Hospitalization prolonged	xxx (xx.x)	xxx (xx.x)	xxx	xxx
Disability / incapacity	xxx (xx.x)	xxx (xx.x)	xxx	xxx
Congenital anomaly	xxx (xx.x)	xxx (xx.x)	xxx	xxx
Others	xxx (xx.x)	xxx (xx.x)	xxx	xxx
Action taken, n (%)				
None	xxx (xx.x)	xxx (xx.x)	xxx	xxx
Modified to 100mg OD	xxx (xx.x)	xxx (xx.x)	xxx	xxx
Temporarily interrupted	xxx (xx.x)	xxx (xx.x)	xxx	xxx
Permanently discontinued	xxx (xx.x)	xxx (xx.x)	xxx	xxx
Unknown	xxx (xx.x)	xxx (xx.x)	xxx	xxx
Treatment related, n (%)				
Not related	xxx (xx.x)	xxx (xx.x)	xxx	xxx
Unlikely related	xxx (xx.x)	xxx (xx.x)	xxx	xxx
Possibly related	xxx (xx.x)	xxx (xx.x)	xxx	xxx
Probably related	xxx (xx.x)	xxx (xx.x)	xxx	xxx
Definitely related	xxx (xx.x)	xxx (xx.x)	xxx	xxx
Unknown	xxx (xx.x)	xxx (xx.x)	xxx	xxx
Outcome, n (%)				
Recovered	xxx (xx.x)	xxx (xx.x)	xxx	xxx
Recovered with sequelae	xxx (xx.x)	xxx (xx.x)	xxx	xxx
Ongoing	xxx (xx.x)	xxx (xx.x)	xxx	xxx
Death	xxx (xx.x)	xxx (xx.x)	xxx	xxx
Unknown	xxx (xx.x)	xxx (xx.x)	xxx	xxx
Withdrawn due to SAE, n (%)				
Yes	xxx (xx.x)	xxx (xx.x)	xxx	xxx
No	xxx (xx.x)	xxx (xx.x)	xxx	xxx
Causality, n (%)				
Study treatment	xxx (xx.x)	xxx (xx.x)	xxx	xxx

Disease under study	xxx (xx.x)	xxx (xx.x)	xxx	xxx
Other illness	xxx (xx.x)	xxx (xx.x)	xxx	xxx
Concurrent medication / treatment	xxx (xx.x)	xxx (xx.x)	xxx	xxx
Others	xxx (xx.x)	xxx (xx.x)	xxx	xxx
Unknown	xxx (xx.x)	xxx (xx.x)	xxx	xxx

SAE: serious adverse event.

Note: Under number of events, the same SAE term of multiple SAE criteria, actions, relationships, outcomes and causalities reported by a single subject will be counted separately. Under number of subjects, only unique subjects will be counted.

Table 11: Adverse events by system organ class and severity grade

Population: Safety population

System Organ Class Preferred Term	MILD			MODERATE			SEVERE			UNKNOWN		
	n (%)	nAE	n (%)	n (%)	nAE	n (%)	n (%)	nAE	n (%)	n (%)	nAE	n (%)
Aspirin (N = xxx)												
System organ class 1	xx (xx.x)	xx	xx (xx.x)	xx	xx	xx (xx.x)	xx	xx	xx (xx.x)	xx	xx	xx (xx.x)
Preferred term 1	xx (xx.x)	xx	xx (xx.x)	xx	xx	xx (xx.x)	xx	xx	xx (xx.x)	xx	xx	xx (xx.x)
Preferred term 2	xx (xx.x)	xx	xx (xx.x)	xx	xx	xx (xx.x)	xx	xx	xx (xx.x)	xx	xx	xx (xx.x)
Preferred term 3	xx (xx.x)	xx	xx (xx.x)	xx	xx	xx (xx.x)	xx	xx	xx (xx.x)	xx	xx	xx (xx.x)
...	xx (xx.x)	xx	xx (xx.x)	xx	xx	xx (xx.x)	xx	xx	xx (xx.x)	xx	xx	xx (xx.x)
System organ class X	xx (xx.x)	xx	xx (xx.x)	xx	xx	xx (xx.x)	xx	xx	xx (xx.x)	xx	xx	xx (xx.x)

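### Table 11 appears to have no any-severity column, so the number of patients with an AE term or organ class seen at two or more severities is known only as a range

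*SAP*

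**What the plan says.** SAP 4.7 Safety Endpoints sets two counting rules for AEs. The same term at several severities in one subject "will be counted for each level of severity, not just the highest severity". Then: "Under subject counts at each severity category, only unique subject will be counted". A subject is thus unique within a severity but can appear under more than one.

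The shells in SAP Appendix 1 apply these rules as follows.

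- "Table 11: Adverse events by system organ class and severity grade" is the only table of all AEs by organ class and preferred term. Its visible column headings are Mild, Moderate, Severe and Unknown, each with a subject count and an event count.
- Table 9 has a top row for subjects with any AE, with the note "Under number of subjects, only unique subjects will be counted". That count is for the whole arm, not by term.
- Table 1 has a block headed "Subjects discontinued study treatment, n" (%), with AE/SAE as one reason. Table 9 counts permanent discontinuations. Neither is by term.
- Table 12 gives SAEs by class and term. Table 13 does the same for severe related AEs. Table 14 covers six named medical events.
- The only AE listing by subject is for SAEs.

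For bleeding, Protocol 11.7 says: "Major gastrointestinal bleeding (requiring blood transfusion) will also be recorded". SAP 4.7 uses the same transfusion condition for the Table 14 entry.

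**The concern.** The usual first question of an AE table is how many patients in each arm had the event at all. With overlapping severity columns and no total, Table 11 does not answer it for any row that is filled at two or more severities.

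Overlap is plausible in this trial. Protocol 11.3 states: "3-monthly patient assessments will be done at month 3, 6, 9, 12, 15, 18, 21, 24, 27, 30, 33, and 36", and AEs are recorded at each of these visits. Protocol 9.2 grades epigastric discomfort as mild, moderate or severe. After a mild episode the drug continues at 100 mg. After a moderate one the guidance is: "Rechallenge with lower dose (i.e. 100 mg) of study drug if symptoms resolved and continue long term PPI therapy". One patient can therefore report the term at two grades over three years. In an organ-class row, overlap also arises when a patient has different terms at different grades.

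Protocol 13.1 names gastrointestinal events, mostly minor, as the AEs most expected with aspirin. These are largely non-serious, so Tables 12 to 14 will not capture most of them. A gastrointestinal bleed that is neither serious nor transfused is also outside Tables 12 and 14. It appears by term in Table 11, and in Table 13 only if it is severe and related. If it leads to stopping the drug, it adds to the discontinuation totals in Tables 1 and 9 without its term.

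**Working it through.** The plan gives no figure to reproduce here. The check sets the counting rule against the shell and then works out what a reader could recover from a row.

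**Does the shell lack a total?** Four severity headings are visible. In the text extracted from the PDF, the later placebo rows of Table 11 hold eight cells, which is 4 severities × 2 (subjects and events). The aspirin rows and the first placebo rows hold twelve cells, five of them subject counts. Twelve fits neither 4 × 2 = 8 nor 5 × 2 = 10, so those rows are damaged and do not show a fifth pair. No total heading is visible, and the SAP's list of tables names no other table of all AEs by term.

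**Bounds for one row.** Let the severity columns hold n1 to n4 subjects.

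- Lower bound = max(n1, ..., n4), reached when everyone in the smaller columns is also in the largest.
- Upper bound = n1 + ... + n4 (at most N), reached when nobody is in two columns.
- If only one column is filled, the bounds coincide and the count is exact. For example, 30/0/0/0 means exactly 30 patients.

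**Illustration.** N per arm is 1587/2, taken as 793, with all subjects assumed dosed. The column counts (mild/moderate/severe, none unknown) are assumed. The documents give none.

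- Aspirin 40/24/6: 40 to 70 patients, 40/793 = 5.0% to 70/793 = 8.8%.
- Placebo 26/14/4: 26 to 44 patients, 26/793 = 3.3% to 44/793 = 5.5%.

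**Equal overlap in both arms.** Let v be the share of the maximum possible overlap that occurs, from 0 to 1. Aspirin patients = 70 - 30v, placebo patients = 44 - 18v, and risk difference = (26 - 12v)/793.

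| v | Aspirin | Placebo | Risk difference | Treated per extra patient affected | Risk ratio |
|---|---|---|---|---|---|
| 0 | 70 | 44 | 26/793 = +3.3 points | 31 | 1.59 |
| 0.5 | 55 | 35 | 20/793 = +2.5 points | 40 | 1.57 |
| 1 | 40 | 26 | 14/793 = +1.8 points | 57 | 1.54 |

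**Unequal overlap.** The extremes pair one arm's lower bound with the other's upper bound:

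- full overlap on aspirin, none on placebo: (40 - 44)/793 = -0.5 points
- no overlap on aspirin, full on placebo: (70 - 26)/793 = +5.5 points

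**The case against.** The strongest reply is that little of importance is lost. Per-patient counts exist for any AE overall, SAEs by term, severe related AEs by term, and the named events, including major gastrointestinal bleeding and haemorrhagic stroke. Within each severity, Table 11 counts unique subjects, so the arms can be compared validly at that grade. The SAP also says in general terms that AEs will be summarised by class and term. The tables are mock-ups, and a total could be added at reporting without contradicting the text. All of this stands. It limits the point to an unspecified column for mainly non-serious events. It does not supply the missing count, and the SAE-only listing gives no way to resolve the overlap by hand.

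Four stronger readings are tempting and not supported.

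- A reader might infer that the counting rule is wrong. It is not. Each severity column is a valid count. Only the total is missing.
- A reader might infer that the direction of an arm difference is safe, or that it is likely to reverse. In the illustration the sign is fixed only under equal overlap. It reverses only near one extreme of unequal overlap. The documents do not say how often one patient reports a term at two grades, or whether the arms differ in this.
- A reader might infer that every gastrointestinal bleed ends study drug and so reaches the discontinuation totals. Protocol 9.2 says such patients should stop without rechallenge, but introduces its modifications as reference guidance subject to clinical judgement. Stopping is the expected practice, not a certainty.
- A reader might ask for a separate row for any bleeding AE. That is a different request and does not follow from the missing column.

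**Conclusion.** The point holds as a minor reporting gap. Under the plan as written, a Table 11 row filled at two or more severities gives only a range for the number of patients affected. Rows filled at one severity are exact.

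In the illustration, the aspirin incidence could be anywhere from 5.0% to 8.8%. The risk difference changes nearly twofold under equal overlap, while the risk ratio barely moves. If overlap may differ between arms, the recoverable range for the difference includes zero.

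These sizes rest on assumed column counts and on 793 dosed patients per arm, so they show the mechanism and do not predict a result. The reading of the shell rests on four visible headings and the intact rows of a partly damaged table. It should be confirmed against the PDF. Efficacy analyses and trial conduct are not affected.

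**What to change.** In SAP 4.7, add one sentence: besides the severity breakdown, each subject is counted once per preferred term and once per organ class regardless of severity. In Table 11, keep the existing columns and add an 'Any severity' n (%) column in each arm.

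The AE records needed are already collected, so no new data or visits are required. The cost is a slightly wider table. Specifying the column before unblinding makes this count a planned output.

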9. TREATMENT SCHEDULE

9.1. Treatment groups

The study drug, oral Aspirin 200 mg/ placebo 200 mg OD should be started immediately but no later than 2 weeks after randomisation/baseline visit. The patient will be treated with the same study drug for 3 years.

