9.4. Study Withdrawal

All patients, including patients discontinued from study treatment, will continue to be followed up for 5 years after randomisation, unless the patient withdraws consent, is lost to follow up or death. The reason for withdrawal should be documented.

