11.8 Post Month 60 – Clinical Data

Subjects who have consented to allow data collection after month 60, will have their medical records reviewed every 12 months (or via phone contact), up to and at the time of the last patient last visit (month 60 or earlier) - at the site.

The following will be recorded:

- Death related information; if any
- Medical Events: (AMI, transient ischemic attack, stroke, new cancers and gastrointestinal bleeding)
- Concomitant NSAIDs
- Recurrence and salvage chemotherapy

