13.2 Reporting of Adverse Event

All AEs will be recorded on the AE form in the subject's case report form.

The site investigator (international site or local site) is responsible to report **all SAEs** with de-identified relevant reports **within 1 working day** of the knowledge of the event to all of the following:

- Attention to monitor or project coordinator
- Investigational Product Manufacturer (Bayer AG)

The site investigator is also responsible to report all SAEs to relevant ethics committee or institutional review board within the required timeline. All SAEs will be followed up until resolution with updated information reported whenever available to the relevant parties as per initial reporting procedure.

The study monitor/project coordinator will notify the study co-chair and study project manager with the submitted SAE report by the site. The study co-chair will review the SAE report and recommendations will be sent to the site investigators if any.

The study co-chair is responsible to ensure any serious and unexpected adverse drug reaction occurring in the study is notified to all participant sites for reporting to ethics committee(s) or institutional review board(s) of all study centres and regulatory body (ies) of the country (ies) where the study is conducted by using the CIOMS Form. Fatal or life-threatening unexpected adverse drug reaction must be notified immediately but no later than 7 calendar days after the first knowledge by the study co-chair, followed by a complete report within 8 additional calendar days. All other serious, unexpected adverse drug reactions that are not fatal or life threatening must be reported within 15 calendar days after first knowledge by the study co-chair. The CIOMS Form will be sent to Bayer AG for review before distributing to all participating sites.

After discontinuation of treatment, patients should be carefully monitored for the occurrence of new adverse events up to 30 calendar days (follow-up period) after the administration of the last dose of aspirin. Adverse events are to be assessed in terms of their seriousness, severity, and relationship to the study drug. Only serious adverse (SAEs) should be reported to Bayer AG.

AEs and SAEs will be recorded from the time of entry into the study until 30 days after the full completion of study treatment, or in instances of early drug termination 30 days after the final cessation of study drug.

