4 STATISTICAL ANALYSIS

4.1 General

Continuous variables will be summarised using descriptive statistics, i.e., mean, standard deviation, median, interquartile range (IQR), minimum and maximum. Categorical variables will be summarised by frequency and percentage. All statistical significance tests and confidence intervals are two-sided. A p-value <0.05 is considered statistically significant. All confidence intervals (CIs) are at 95% level. All statistical analyses will be conducted using SAS version 9.2 or higher (Statistical Analysis System software, SAS Institute, North Carolina, USA).

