Yes	xx (xx.x)	xx (xx.x)	
No	xx (xx.x)	xx (xx.x)	
Major nervous system bleeding			0.xxx
Yes	xx (xx.x)	xx (xx.x)	
No	xx (xx.x)	xx (xx.x)	

n: number of subjects; %: percentage of randomised in each treatment group; GI: gastrointestinal bleeding.
¹Fisher's exact test.

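### The only formal comparison of bleeding and vascular events pools on-drug and off-drug time, which dilutes the risk ratio and the test but leaves the risk difference almost unchanged

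*SAP*

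**What the plan says.** SAP 4.7 names six medical events: acute myocardial infarct, ischaemic stroke, new non-colorectal cancer, major gastrointestinal bleeding needing transfusion, haemorrhagic stroke and, closing the list, "major nervous system bleeding throughout the study will be counted and its corresponding percentages will be respectively compared between the two treatment groups". The method is Fisher's exact test. Under SAP 4.1, "A p-value <0.05 is considered statistically significant". SAP Table 14 has yes/no rows and a p-value for each event. It has no treatment window, person-time, effect estimate or confidence interval.

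The time frame comes from several places:

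- Protocol 9.1, on treatment: "The patient will be treated with the same study drug for 3 years".
- Protocol 9.4, on follow-up: "All patients, including patients discontinued from study treatment, will continue to be followed up for 5 years after randomisation", with exceptions for withdrawn consent, loss to follow-up and death.
- Protocol 11.4 lists medical events at months 42, 48, 54 and 60, all after the planned end of drug.
- Protocol 11.8 continues yearly collection of medical events in a subset: "Subjects who have consented to allow data collection after month 60".
- SAP 4.9 sets a minimum follow-up of 1 year at the final analysis, so observation time differs between subjects.

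Adverse events follow a different rule in Protocol 13.2: "AEs and SAEs will be recorded from the time of entry into the study until 30 days after the full completion of study treatment", or 30 days after final cessation if drug stops early.

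Table 14 is headed as a safety-population table, but its footnote defines the percentage as "percentage of randomised in each treatment group".

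**The concern.** Major gastrointestinal and intracranial bleeding is the main harm to set against any gain in disease-free survival. If aspirin raises bleeding risk while it is taken, the extra events fall in the first 3 years. Counting for 5 years or more adds background bleeds to both arms. The ratio of the two percentages moves towards 1, and Fisher's test has more noise to overcome. Anyone forming a risk ratio from Table 14, or reading a non-significant p-value as reassurance, would get a weaker picture of the on-drug effect than the same data could give.

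A crude proportion also takes no account of how long each subject was observed. Subjects with little more than a year and subjects followed past month 60 contribute equally to the denominator.

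**Working it through.** **The plan's own figure.** The documents give no sample size or power for the bleeding comparison. The only design figure is 300 disease-free survival events for a hazard ratio of 0.72, two-sided 5%, 80% power. It reproduces closely: 4 × (1.960 + 0.842)² / (ln 0.72)² = 291 by Schoenfeld's formula, and 297 by Freedman's. Nothing below depends on it.

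**Inputs from the documents.**
- Excess of major gastrointestinal bleeding on aspirin, e = 0.12% per year (Protocol 7.8).
- Planned time on drug, D = 3 years (Protocol 9.1).
- Scheduled follow-up, T = 5 years (Protocol 9.4).
- 1587 subjects randomised 1:1, about 793 per arm (SAP 3.2, Protocol 6).

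**Assumptions, not in the documents.** Placebo rate b = 0.06% to 0.20% per year; background rate constant and equal in both arms; full 3-year adherence; no censoring before T.

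**Risk ratio.** On drug, RR = (b + e)/b. Over the whole count, RR = (bT + eD)/(bT) = 1 + (e/b)(D/T). The excess relative risk is multiplied by D/T = 3/5, a 40% reduction whatever b is.

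| b (% per year) | RR on drug | RR counted to 5 years |
|---|---|---|
| 0.06 | 0.18/0.06 = 3.0 | (0.30 + 0.36)/0.30 = 2.2 |
| 0.12 | 0.24/0.12 = 2.0 | (0.60 + 0.36)/0.60 = 1.6 |
| 0.20 | 0.32/0.20 = 1.6 | (1.00 + 0.36)/1.00 = 1.36 |

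The 40% applies to subjects who take drug for 3 years and are observed for 5. With 4 years observed it is 1 − 3/4 = 25%. With 2 years on drug and 5 observed it is 1 − 2/5 = 60%. A subject still on drug at last contact contributes no dilution.

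**Risk difference.** The absolute excess is eD = 0.12 × 3 = 0.36 percentage points, whatever T is. That is 793 × 0.0036, or about 3 extra bleeds in the aspirin arm. Exponential risks give the same answer: at b = 0.10%, 0.66% against 0.30% at 3 years (RR 2.20) and 0.86% against 0.50% at 5 years (RR 1.72), with a difference of 0.358 points both times.

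**Power of the planned test.** Fisher's test was enumerated exactly with 793 per arm at two-sided 0.05, counting significance only towards more bleeding on aspirin.

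| Case | 3-year count | 5-year count |
|---|---|---|
| Major GI bleeding, e = 0.12%, b = 0.10% | 8.6% | 7.6% |
| Major GI bleeding, e = 0.12%, b = 0.20% | 7.2% | 6.1% |
| Assumed larger signal: on-drug rate ratio 3, b = 0.3% | 71% | 58% |

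For major gastrointestinal bleeding, power stays between about 4% and 9% for b from 0.05% to 0.5% per year and counts of 3, 5 or 8 years. For intracranial haemorrhage (0.03% per year in Protocol 7.8) it is about 2% or less.

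**The case against.** **On-drug bleeding is already displayed.** Adverse events are recorded only until 30 days after drug, so SAP Tables 9 to 13 are close to on-treatment summaries by arm, including system organ class and preferred term. SAP 4.7 also lists serious events with onset dates, and a transfused bleed or haemorrhagic stroke would normally qualify as serious. This stands: a reader might infer that on-treatment bleeding goes unreported, and the documents do not support that. Those tables lack person-time, an effect estimate and a between-arm comparison, so Table 14 remains the only formal one.

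**The absolute difference is not diluted.** This also stands, and absolute risk is what one weighs against benefit. A reader might infer that the plan hides or understates aspirin's harm. It does not: Table 14 plans no relative risk and does not claim to be an on-treatment analysis, and the difference between its percentages is nearly the same in any window. The caveat is that off-drug rates must be equal in the two arms. Protocol 10 bars antiplatelets and anticoagulants only alongside study drug, so later use could blur the difference.

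**Whole-study counting is legitimate.** It preserves the randomised comparison, and Protocol 4 gives persistence of effect after treatment as one purpose of the 5-year follow-up. A reader might conclude that an on-treatment comparison should replace it. Protocol 9.2 and 9.3 provide for stopping drug for bleeding, recurrence and related serious events, so exposure can differ by arm and stopping can be informative. That supports adding a treatment-period analysis, not substituting one.

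**The test is weak in any window.** True at the protocol's rates. A narrower window improves the estimate of the on-drug ratio; it does not produce a well-powered test.

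**Conclusion.** The concern holds as a limited gap in the safety analysis. The one formal comparison of bleeding and vascular events ignores both exposure and unequal follow-up. Under the stated assumptions, a major gastrointestinal bleeding risk ratio of 3.0 to 1.6 on drug appears as 2.2 to 1.36 at 5 years. The 40% loss of excess relative risk needs only the protocol's 3-year and 5-year periods, full adherence and a constant background rate; the ratios themselves also need the assumed placebo rate.

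The loss of power is about one percentage point at the protocol's excess and becomes material only for a larger signal, which the documents do not posit. The dilution beyond month 60 cannot be sized from the documents, because it depends on accrual and on how many subjects consent to later collection. The validity of the randomised comparison is not in question. Separately, the Table 14 footnote contradicts its own heading, SAP 4.2 and the statement in SAP 4.7 that safety presentations use subjects as actually treated.

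**What to change.** Keep the whole-study Table 14 comparison and make three changes.

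1. Add a prespecified treatment-period analysis of the medical events in the safety population, from first dose to last dose plus 30 days. Report rates per 100 patient-years, the rate ratio and rate difference with 95% confidence intervals, and cumulative incidence with death as a competing risk. Label it supplementary.
2. Give the whole-study comparison an effect estimate and confidence interval by a method that allows for unequal follow-up, beside the Fisher p-value.
3. Align the Table 14 footnote with the safety population.

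The cost is a little programming. The 30-day window is already in Protocol 13.2, the dosing dates are already needed for the exposure formula in SAP 2, and a competing-risks model is already planned in SAP 4.6. Dates of medical events must be confirmed as held. The treatment-period analysis will have fewer events and wider intervals, and informative stopping may bias it, so it should be read with the whole-study result and not in place of it.
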